8.7. Screening Assessments

See [Table 4](#) for the list of assessments that are routine plasma donor screening and/or testing assessments and those that are considered part the clinical trial data that will be reported on an eCRF and will be included in the data analysis and final clinical study report.

After signing informed consent to the study, subject screening for eligibility will occur over a 7-day period (Study Days -7 to -1). The following procedures will be performed to assess subject eligibility and to collect other baseline or plasma donor suitability screening data:

- Demographics
- Medical history
- Immunization record and medications used within the past 7-days
- Pre-donation screening examination including:
 - Agree to contraceptive use for women of child-bearing potential for the duration of the study
 - Vital signs
 - Infectious disease screening of donor plasma, tetanus antibody test of donor plasma, hematocrit and total protein
 - Full physical examination for new donors (this is waved for donors of record who have had a full physical examination during the last year)
- Body weight
- Review eligibility checklist

8.8. Procedures Performed on Vaccination Days

Procedures on vaccination days and at the next visit within 1 to 3 days after each vaccination at Months 0, 3, 6, 9, and 12 unless otherwise noted will be performed in the following order:

- Pre-donation screening examination (see [Table 4](#)). Review of diary card and open ended question for AEs (not performed at Month 0); however, explanation of the use of the diary card will be performed at the Month 0 visit
- Confirm eligibility for plasmapheresis
- Perform plasmapheresis and collect plasma sample for anti-tetanus and anti-diphtheria antibody titer tests (not performed at Month 0) and plasma for infectious diseases
- Administer vaccine (ensure that all study participants continue to meet study eligibility criteria prior to each vaccination)
- Closely observe study participants for 30 minutes after each vaccination for immediate adverse reactions per standard practice
- Query subject about AEs before leaving the center
- Perform a dip-stick urinalysis and serum creatinine from 1 to 3 days after each vaccination. If the subject does not return to the center within this time frame, the sample should be collected and tested at the next visit to the center (typically within one week for the next plasma donation).

8.9. Procedures Performed During Visits Between Vaccinations

Visits at Months 1, 2, 4, 5, 7, 8, 10 and 11 will have the following procedure performed:

- Collect and freeze plasma for anti-tetanus and anti-diphtheria antibody titer tests

- Diary review and AE questions

Note: plasma donations and pre-donation screening procedures are also conducted at these visits as part of routine donor visits

8.10. Follow-up Post Completion of Vaccinations

At Study Months 13 and 18, the subject will visit the study center and have the following procedures performed:

- Pre-donation screening examination (see [Table 4](#)).
- Medication review
- Review of birth control methods for women of childbearing potential and obtain verbal report of pregnancy status
- AEs and diary card review
- Perform plasmapheresis and collect plasma sample for anti-tetanus and anti-diphtheria antibody titer tests
- Query subject about AEs before leaving the center

8.11. Subject Withdrawal Criteria

A subject can withdraw from the trial at any time. The subject should contact the Investigator immediately and notify him/her that they are leaving the study. If possible, the reason for withdrawal for all subjects who do not complete the 12-month treatment period will be recorded.

The Investigator may withdraw a subject from the study in the following cases:

- For safety reasons, such as a severe or serious AE, that does not justify continuation in the study in the opinion of the Investigator;
- For a protocol violation that jeopardizes the performance of the study;
- The subject does not comply with the protocol;
- The subject no longer qualifies as a plasma donor;
- Continued participation will pose a risk to the subject; or,
- Pregnancy.

In the event of subject withdrawal, site personnel should attempt to collect the subject's study diary (completed through the day of withdrawal, if available).

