Medical history ^e	X	X	X	X	X	X	X	X	X	X	X	X	X	
Body weight	X	X	X	X	X	X	X	X	X	X	X	X	X	
Infectious diseases ^f	X													
Immunization record	X													
Medications	X	X	X	X	X	X	X	X	X	X	X	X	X	
Pre-donation screening examination ^g	X	X	X	X	X	X	X	X	X	X	X	X	X	
Plasmapheresis			Plasma donations may occur 2-times per week with at least one-calendar day between donations.											

^a At screening, the reasons a subject is not eligible for the study (screen failure) will be captured on a Reasons Not Eligible eCRF. Subjects will be checked to ensure that they meet study eligibility criteria prior to each vaccination. If not eligible, a Reasons not Eligible for Vaccination eCRF will be completed.

^b Tetanus and diphtheria antibody test samples will be collected, frozen and tested at a later date. Samples are collected from plasma donations performed at these visits. If a plasmapheresis was not scheduled or performed at this visit (\pm 1 week) then a blood sample collected for plasma separation may be used instead.

^c Serum creatinine and urinalysis - measured 1-3 days after each study vaccination. If the subject does not return to the center within this time frame, the sample should be collected and tested at the next visit to the center.

^d The subject's diary card will be reviewed at each monthly visit for recording of AEs and medications.

^e Medical history is updated at all visits after the screening visit including reports of pregnancy by female participants.

^f Anti-HIV-1/2, HBsAg, Anti-HCV, SPE/RPR, Indirect Coombs, and PCR testing for HIV-1, HBV and HCV, HAV, Parvovirus B 19 are tested from plasma samples collected from two sequential plasma donations and must be negative for a subject to be eligible for the study. Infectious disease testing is also performed on plasma samples collected from plasma donations and if a subject is positive for any of these infectious diseases, they will be taken off study. In addition, RPR (syphilis test) is performed every 4 months.

^g Pre-donation screening assessments include a full physical exam performed annually, vital signs and hematocrit and total protein at each donation. If the subject is already a donor of record, the full physical examination will only be performed when regularly scheduled.

Table 4 Continued: Time and Events Schedule

	Follow-Up 1	Follow-Up 2
Month	13	18
Visit Number	20	21
Medications	X	X
AEs	X	X
Plasma sample for anti-tetanus and anti-diphtheria antibody titer	X	X

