Diary card review	X	X
Subject disposition		X
Medical history	X	X
Body weight	X	X
Medications	X	X
Pre-donation screening examination	X	X
Subject Disposition ^a		X

^a The final disposition of the subject will be reported on a Subject Disposition eCRF including if the subject completed the full study or withdrew early and the reason for early withdrawal. This eCRF will be completed at an earlier visit if the subject withdrew from the study.

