11.2.8.3.4. Outcomes and Actions Taken

All unresolved AEs will be followed for a minimum of 7 days (unless the AE is an ongoing pregnancy which must be followed to conclusion) after the subject's final study visit, unless the investigator's judgment dictates otherwise, the event has resolved or stabilized prior to the 7-day period, or the subject is lost to follow-up.

Investigators are not obligated to actively seek AEs or SAEs in former study subjects that occur following the follow-up period.

For each recorded AE or SAE, the investigator must make an assessment of outcome at the time of last observation, as follows:

Fatal:	The subject died
Resolved without Sequelae:	The AE or SAE has ended
Resolved with Sequelae:	The AE or SAE has ended but changes are noted from baseline
Unresolved – Ongoing:	The AE has not ended and is ongoing at the end of the reporting period (i.e., 7 days after the final Follow-up visit) and the investigator deems that further follow up is not medically required
Unknown – Lost to Follow-up:	Lost to follow-up after repeated unsuccessful attempts to contact the subject

Actions taken with respect to investigational agents (discontinuation or not) will also be recorded. In addition, if the AE was treated (medications or other physical measures), this will also be recorded.

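### Withdrawal is from the study, with no exit visit and no planned collection of new adverse events afterwards, so the overall safety tables can under-count later events

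*Protocol*

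**What the plan says.** **Grounds for exit.** Protocol section 8.11 introduces its list with "The Investigator may withdraw a subject from the study in the following cases". The list includes "For safety reasons, such as a severe or serious AE, that does not justify continuation in the study in the opinion of the Investigator" and "The subject no longer qualifies as a plasma donor". Both are discretionary. One ground is mandatory: footnote f to Table 4 in section 6.1 says "if a subject is positive for any of these infectious diseases, they will be taken off study", and section 11.2.4 and SAP section 5.3 repeat it.

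**Data at exit.** Section 8.11 asks staff to try to obtain the diary, "completed through the day of withdrawal, if available". The note on the disposition form under Table 4 adds "This eCRF will be completed at an earlier visit if the subject withdrew from the study". No safety assessments are attached to that visit, and Table 4 has no early-termination column.

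**Data after exit.** Section 11.2.8.3.4 states "All unresolved AEs will be followed for a minimum of 7 days" after the final study visit. Pregnancy is followed to conclusion, and there are exceptions for investigator judgment, earlier resolution and loss to follow-up. The same section says "Investigators are not obligated to actively seek AEs or SAEs in former study subjects that occur following the follow-up period", but it does not define that period for someone who left early. The AE window (11.2.8.1.1) and the SAE window (11.2.8.4.1) run to the last follow-up visit and do not mention withdrawal.

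**Analysis.** The safety endpoint (section 9.2) covers each interval between vaccinations and the whole study. SAP section 4 uses the ITT set, meaning anyone given any vaccine, for safety. The SAP's AE tables are counts and percentages of subjects. SAP section 10 imputes no missing data and gives no rule for shortened AE follow-up.

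**The concern.** Safety is the primary objective, and part of the endpoint is AE incidence over the whole study period. A subject withdrawn early is still counted in the overall ITT denominator, but nobody is scheduled to ask that subject about new events. In a crude percentage, not observed and event-free look the same.

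If exit is unrelated to later risk, this costs information and pulls the overall percentage down somewhat. If exit follows an AE, the subjects no longer observed may be those at higher risk of a further event, and the shortfall becomes informative. The study tests a schedule more frequent than the licensed one, so events that appear after a poorly tolerated dose matter to its conclusion.

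The protocol itself points to effects that need not show within days. Section 4.4 refers to Guillain-Barré syndrome within 6 weeks of a tetanus toxoid vaccine. Section 11.2.6 monitors for immune complex-mediated glomerular disease.

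**Working it through.** **1. Planned follow-up, reproduced.** Protocol section 6.4 gives 12 months of vaccination plus 6 months of follow-up: 12 + 6 = 18 months per subject. With the synopsis's 4 months of recruitment, 18 + 4 = 22 months. Both agree with the protocol. The sample size of 100 has no stated power, precision or dropout input, so there is nothing to reproduce there.

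**2. What remains if a subject exits just after a dose.** Months remaining = 18 − month of dose. The 7-day minimum is 7 / 30.4375 = 0.23 month, and it covers only AEs already open at exit.

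| Last dose | Month | Planned months remaining | 7 days as share of remainder |
|---|---|---|---|
| 1 | 0 | 18 | 1.3% |
| 2 | 3 | 15 | 1.5% |
| 3 | 6 | 12 | 1.9% |
| 4 | 9 | 9 | 2.6% |
| 5 | 12 | 6 | 3.8% |

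For new-onset AEs the planned collection over the same span is nil.

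**3. Effect on a crude percentage.** This shows direction and is not an estimate. Assume 100 ITT subjects, of whom w exit before a late risk period. Assume late-event risk r = 2% in those who stay and q in those who exit, with nothing recorded after exit.

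- True percentage = [w × q + (100 − w) × r] / 100
- Reported percentage = (100 − w) × r / 100

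| w | Reported | True, q = 2% | True, q = 10% | True, q = 30% |
|---|---|---|---|---|
| 5 | 1.9% | 2.0% | 2.4% | 3.4% |
| 10 | 1.8% | 2.0% | 2.8% | 4.8% |
| 20 | 1.6% | 2.0% | 3.6% | 7.6% |

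For w = 10 and q = 10%: true = (10 × 0.10 + 90 × 0.02) / 100 = 2.8%, and reported = 90 × 0.02 / 100 = 1.8%. With q = r the shortfall is small. It grows when exit is tied to risk. None of w, q or r is in the documents.

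**4. What follow-up to 6 months after the last dose would restore.** After doses 1 to 5 it recovers 6 of 18, 6 of 15, 6 of 12, 6 of 9 and 6 of 6 months, that is 33%, 40%, 50%, 67% and 100% of the remainder. It gives early stoppers the same post-dose window as completers. It does not give them the full 18 months.

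**The case against.** The strongest reply is that the plan is less bare than it looks.

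- Withdrawal for an AE or for donor status is at the investigator's discretion.
- A missed dose need not mean exit. Footnote a to Table 4 has a form for ineligibility for a vaccination, and SAP section 5.1 has codes for drug discontinued or interrupted. SAP Table 5 has a temporary ineligibility category, and footnote b lets a blood sample replace a donation.
- The AE that prompts exit is recorded, counted at its worst severity, and shown in SAP Listing 13.
- Solicited AEs are collected for only 3 days after each dose, so most reactogenicity to a given dose is seen before exit.

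All of this is correct, and it rules out three stronger readings that a reader might infer.

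1. That AE data stop on the day of withdrawal. The quoted phrase concerns the diary only; open AEs get at least 7 more days, and pregnancies are followed to conclusion.
2. That the plan knows no state other than study withdrawal. The forms and codes above show otherwise.
3. That a severe AE removes a subject automatically. Only a positive infectious disease test does.

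The gap itself remains. Those forms and codes are data fields with no follow-up schedule attached for a subject who has stopped vaccination. The AE and SAE windows neither close at withdrawal nor say that they stay open, so sites must decide for themselves. New-onset unsolicited events after exit remain uncollected by plan.

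**Conclusion.** The point holds in this limited form and should be corrected. Once a subject is withdrawn, the protocol plans no exit visit and no collection of new AEs, while the analysis keeps the subject in the overall ITT denominator. The events at risk are new, unsolicited ones after exit. The loss is informative where an AE led to the exit.

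The same cannot be said of exits for donor status or a positive infectious disease test. Nothing in the documents links these to the vaccine or to later AE risk, so for them the supported claim is lost follow-up, not informative loss.

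The total size cannot be stated. A reader might assume 20% to 40% withdrawal at a constant rate over 18 months. Mean follow-up is then 18 × 0.20 / 0.223 = 16.1 to 18 × 0.40 / 0.511 = 14.1 months, or about 10% to 22% lost. The documents do not support using that figure here: the rate is invented, and it covers all withdrawals, including withdrawn consent and loss to follow-up, which no change to section 8.11 would recover. What can be stated is the exposure per withdrawn subject: 6 to 18 months of planned AE follow-up, depending on the last dose received.

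This rests on reading withdrawal from the study as ending the scheduled visits. If sites are meant to keep collecting AEs after withdrawal, the protocol needs to say so.

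**What to change.** Leave every ground for stopping vaccination or donation as it is, and change only what happens to data collection afterwards.

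1. In section 8.11, separate no further vaccination from withdrawal of consent. Make the infectious disease wording consistent, so that removal does not by itself end AE follow-up in a subject who still consents. That wording is in Table 4 footnote f, protocol section 11.2.4, SAP Table A footnote f and SAP section 5.3.
2. For subjects who stop vaccination or donation without withdrawing consent, keep collecting AEs, SAEs and medications at the scheduled contacts, by telephone if they are not donating, until at least 6 months after the last dose. That point falls on a scheduled visit after doses 1, 2, 3 and 5 (Months 6, 9, 12 and 18). After dose 4 it is Month 15, between the Month 13 and Month 18 visits, so use Month 18 or add one call.
3. In sections 11.2.8.1.1 and 11.2.8.4.1, state that the AE and SAE windows apply to these subjects.
4. In the SAP, include these data in the ITT safety tables. Because follow-up will still differ between subjects, add AE rates per person-time beside the crude overall percentages.

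The cost is protocol and consent wording, a small SAP addition, and some extra site time for non-donating subjects. It cannot recover subjects who withdraw consent or are lost to follow-up.

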9. STUDY ENDPOINTS

9.1. Efficacy Endpoints

- Anti-tetanus antibody titer expressed as international units per mL (IU/mL) at each collection point.

- The numbers and percentages of subjects whose post vaccination antibody levels are <5 IU/mL; ≥ 5 IU/mL to 10 IU/mL; >10 IU/mL to 15 IU/mL; and, >15 IU/mL will be presented after each vaccination.

9.2. Safety Endpoints

- Incidence, severity and relationship of AEs to the study vaccine in the time period between vaccinations and for the overall study period.

10. SAFETY MONITORING PLAN

Safety monitoring will be conducted throughout the study; therefore safety concerns will be identified by continuous review of the data by the site investigators, center staff, the clinical monitors, the medical monitor, and the sponsor.

The IRB, medical monitor, investigators, clinical monitors and the sponsor will review any safety concerns throughout the trial. The roles of these individuals/committee are described below.

Medical Monitor: A medical monitor has been appointed for the study. The medical monitor will be available for making recommendations to the investigator and sponsor on the severity of any SAEs, and the relatedness to the study interventions. The medical monitor will also be responsible for tracking and assessing trends in the AEs reported and making recommendations to the investigator for individual subject discontinuations or to the sponsor for study termination.

Clinical Monitors: All investigators will allow clinical monitors from Fast-Track to periodically monitor, at mutually convenient times during and after the study, all study data. These monitoring visits provide the sponsor with the opportunity to evaluate the progress of the study and to obtain information about potential problems. The monitors will assure that submitted data are accurate and in agreement with any paper source documentation used; verify that investigational products are properly stored and accounted for, verify that subjects' consent for study participation has been properly obtained and documented, confirm that research subjects entered into the study meet inclusion and exclusion criteria, and assure that all essential documentation required by Good Clinical Practices (GCP) guidelines are appropriately filed.

Monitors will conduct a site initiation visit prior to the start of the study. At this visit, they will assure that proper study-related documentation exists, assist in training investigators and other site personnel in study procedures and GCP guidelines, confirm receipt of study supplies, and assure that acceptable facilities are available to conduct the study.

Routine monitoring visits by clinical monitors will be scheduled at appropriate intervals. At these visits, the monitors will verify that study procedures are being conducted according to the protocol guidelines, monitor eCRFs against source documents, review AEs and SAEs, and perform drug accountability. At the end of the study, they will confirm that the site has the appropriate essential documents on file, advise on storage of study records, and inspect the return and destruction records for unused investigational products.

11. ASSESSMENT METHODS

11.1. Efficacy Assessments

When plasmapheresis is scheduled during one of the clinical protocol monthly study visits, a sample of the plasma collected during plasmapheresis will be collected. Samples will be stored at $\leq -20^{\circ}\text{C}$ until tested and will be tested throughout the study shortly after collection.

Tetanus antibody responses will be measured at a central laboratory using an enzyme-linked immunosorbent assay (ELISA) [VaccZyme Tetanus Toxoid IgG – Binding Site] and expressed as international units per mL (IU/mL). Samples tested throughout the study and the results will be reported on an eCRF. The electronic results in the form of a de-identified Excel spreadsheet that links the Unit control number to the Subject ID number will be transferred to Fast-Track for inclusion in the main study database for analysis.

11.2. Safety and Other Baseline Assessments

11.2.1. Demographics/Medical History

A complete medical history and demography (gender, age, race, and ethnicity) will be collected at the screening visit and recorded in a source document and reported on an eCRF. The medical history will be updated at monthly visits when plasma donation will be performed including self-reported pregnancy status for women of child-bearing potential.

11.2.2. Prior and Concomitant Medications Including Immunizations

Medications being taken by the subject in the 7-day period prior to the first vaccination through the completion of the study will be recorded and reported on an eCRF. The subject's immunization history will also be collected and reported. In general, concomitant medication use is permitted during the study. However, certain medications may require a washout period prior to plasmapheresis and could result in the deferral of a visit or possible removal of the subject from the study. In addition, immunosuppressive drugs will be prohibited as these can attenuate antibody responses. Epinephrine will be available on site for the treatment of possible anaphylaxis reactions. Subjects will be asked to record medication use to treat an AE in their diary. The name of the medication, start date, stop date or ongoing, dose, route and frequency will be recorded on a source document at study visits and will be reported on an eCRF.

11.2.3. Pre-donation Screening Assessments

Vital signs will be collected as part of the pre-donation screening assessments covered in GCAM / Biomat USA – Grifols SOP Manual in accordance with 21 CFR 630.10 and 36.0.15. Vital signs must meet the following criteria for the subject to be considered eligible for plasmapheresis at all scheduled time points:

- Temperature: 97.0 – 99.5°F
- Blood Pressure: 90–180/50–90 mmHg
- Pulse: 50 – 100 beats/min

Body weight will be measured as part of pre-donation screening and must be > 110 lbs for a subject to be eligible for plasmapheresis.

Blood will be collected in appropriate capillary tubes for hematocrit and total protein determinations as part of the routine plasmapheresis donor screening covered in GCAM / Biomat USA – Grifols SOP Manual. For a subject to be eligible for plasmapheresis, results must fall within the ranges shown below.

- Hematocrit
 - 38 – 54% Females
 - 39 – 54% Males
- Total Protein 6.0 – 9.0 grams/deciliter

A full physical examination will be performed annually as part of the routine plasmapheresis donor screening covered in GCAM / Biomat USA – Grifols SOP Manual in accordance with 21 CFR 640.63. If the subject is a new donor, then they will receive a full physical examination.

The full physical examination includes:

- General overall appearance
- Examine both arms, front and back, for prior venipuncture or “track” marks.
- Examine head, eyes, ears, nose and throat.
 - Head should be normo-cephalic and free of recent abrasions.
 - Eyes - clear without revealing any icterus, conjunctivitis, chalazion, hordeolum, exudate, or pupil abnormalities related to drugs.
 - Free of rhinitis
 - Ears - check for otitis externa, exudate from lobes due to recent ear piercing, and otitis media.
 - Examine neck for lymphadenopathy.
 - Examine mouth - check under tongue for track marks, and look for irregular, cottony appearing white blotches.
 - Heart and lung sounds should be checked both front and back, with several intakes of air. Note rales, chronic, wheezes and abnormal congestion. Any abnormal heart sounds or rhythm irregularities require careful evaluation.
 - Abdominal examination is used to detect enlargement of the liver, spleen or lymph nodes.
 - Neurological exam is to consist of a reflex assessment.
 - Observe gait and inspect for any tremors of the extremities.
 - Test pupillary reactions to light.
 - Test extraocular movements.

General overall appearance and an examination of both arms, front and back, for prior venipuncture or “track” marks will be performed at all other visits.

